Title: The use of a routine indwelling urinary catheter in patients receiving neuraxial anesthesia for elective total joint arthroplasty

PI: [name] [name]

Co-investigators:

[name]

[name]

[name]

[name], BS

IRB Approval # 19123101

NCT #05428020

Document attached: Study protocol

Approved study: 2/21/2020

Approved amended protocol: 10/7/20

ORA: 19123101-IRB03 Date IRB Approved: 2/21/2020 Amendment Date: 10/7/2020

The use of a routine indwelling urinary catheter in patients receiving neuraxial anesthesia for elective total joint arthroplasty

Principal Investigator [name] M.D

Co-Investigators
[name] M.D
[name] M.D
[name] M.D
[name]

Purpose:

Determine whether routine use of a short term indwelling urinary catheter decreases the rate of urinary retention in patients undergoing elective inpatient total joint replacements

Hypothesis:

We hypothesize that the routine use of a short term indwelling urinary catheter will decrease the rate of urinary retention compared to patients who do not receive a urinary catheter.

Background and Introduction:

Urinary retention is a known complication following surgical procedures, with a theoretical increased risk in patients receiving neuraxial anesthesia due to a decreased ability to sense bladder distension. Urinary retention is associated with adverse events including bladder atony, increased post void residuals, and postoperative urinary tract infection. Treatment of urinary retention involves intermittent or indwelling urinary catheter placement, both of which are associated with an increased prevalence of postoperative urinary tract infection.²

There currently is no consensus whether the use of a urinary catheter in elective joint arthroplasty with neuraxial anesthesia decreases the risk of urinary retention. The prevalence of retention reported in the literature varies widely with reports anywhere from 0% to 75% in patients with early removal of a catheter or after procedures performed without a catheter.

At Rush University Medical Center currently, all patients undergoing primary total joint arthroplasty receive neuraxial anesthesia preoperatively and have short term indwelling urinary catheter placed intraoperatively. The urinary catheter is removed when the patient arrives on the orthopedic floor and the Rush urinary retention protocol is followed.

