The need for routine use of indwelling urinary catheters was previously investigated in a randomized controlled trial by Miller et al in 2013 in patients undergoing total hip arthroplasty. They found a 2.8% rate of urinary retention in patients who received a urinary catheter and a 9.7% rate in patients who did not. Although this did not demonstrate statistical significance (P 0.07), they concluded that a routine indwelling urinary catheter is not required. However, Miller et al provided a fairly large time span for urinary catheter use ("removal within 48 hours") and failed to provide any temporal data regarding duration of use. With this in mind, our study will further investigate this conclusion with a goal to identify if routine use of a urinary catheter that is removed on the same day of surgery decreases postoperative urinary retention in patients undergoing elective inpatient total joint replacement.

Study Design

ORA: 19123101-IRB03 Date IRB Approved: 2/21/2020 Amendment Date: 10/7/2020

Prospective, multi-surgeon, single institution, randomized controlled trial

Inclusion Criteria

Any patient >18 years of age scheduled for an inpatient primary hip or knee replacement

Exclusion Criteria

- 1. Patients with a known history of prostate, urological or kidney surgery
- 2. Patients where close monitoring of urine output are necessary during the perioperative period (renal disease, renal failure, chronic indwelling urinary catheter)
- 3. Patients with a history of urinary incontinence
- 4. Patients undergoing a revision total knee or total hip arthroplasty
- 5. Patients requiring indwelling continuous epidural anesthesia
- 6. Patients with a preexisting urinary tract infection, as diagnosed on preoperative screening.
- 7. Patients unable to void prior to surgery as required by anesthesia.

Treatment Groups:

Group 1 (Control): Short term urinary catheter- Patient will receive a urinary catheter at the time of the surgery. The urinary catheter will be removed upon arrival to the orthopedic floor post operatively. Patients will subsequently be monitored for urinary retention according to the Rush University Medical Center urinary retention protocol.

Group 2 (Experimental): No urinary catheter- Patients will not receive a urinary catheter at time of surgery. They will be monitored for urinary retention according to the Rush University Medical Center urinary retention protocol

Sample Size Calculation

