At the time of enrollment in the study, patients will be given a urinary history questionnaire known as the International Prostate Symptom Score (I-PSS) and be asked about history of urinary retention, history of incontinence, and history of polyuria to screen for preexisting urinary issues. Existing pre-operative laboratory testing will be abstracted from the subjects' medical record.

Patients will receive standardized multimodal analgesic regimen that is utilized at Rush University Medical Center for patients undergoing a total joint replacement for perioperative and postoperative pain management. Modifications will be made on a case by case basis as is currently the standard practice (for example, allergy, intolerance, or medical contraindication such as acute kidney injury to NSAID use)

Outcome Measurements:

- 1. Episodes or urinary retention, defined as necessitating 2 straight catheterizations or placement of an indwelling urinary catheter.
- 2. Number of straight catheterizations and volume of urine
- 3. Episodes of indwelling urinary catheter placement in the postoperative course
- 4. Urinary tract infections
 - a. Diagnosed via urinalysis at time of second straight catheterization or urinary placement
 - b. Patients will be asked via questionnaire the following at time of initial follow up to screen for possible urinary tract infection. If screen positive, will order urinalysis and urine culture.⁶
 - Have you had any pain with urination?
 - Have you had an increase in urinary frequency?
 - Have you noticed any lower abdominal pressure with urination?
 - Have you noticed any changes in the color or smell of urine?
- 5. Patient satisfaction (HCAHPS survey) to be administered at initial follow up visit
- 6. Patients who receive a straight catheterization or placement of a urinary postoperatively will be asked via questionnaire a modified version of survey published by Darbyshire et al.⁷
 - a. Was placement of the catheter painful?
 - b. Was placement of the catheter embarrassing?
 - c. Did you know why you were catheterized?
 - d. Did the doctor or nurse talk you through why you were being catheterized?
- 7. Acute periprosthetic joint infections

Risks, Benefits

All surgical patients are at risk of developing urinary retention. To minimize adverse events associated with urinary retention, all patients will be closely monitored according to the Rush University Medical center urinary retention protocol.

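### UTI has no case definition, and no question, data field or record review captures an infection diagnosed and treated before the initial follow-up visit

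*Combined protocol and SAP*

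**What the plan says.** UTI is item 4 of the seven entries under Outcome Measurements. The protocol gives two ways of finding one.

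- **Item 4a, in hospital:** "Diagnosed via urinalysis at time of second straight catheterization or urinary placement". The Urinary retention protocol section likewise sends a urinalysis at the second straight catheterization.
- **Item 4b, at follow-up:** "Patients will be asked via questionnaire the following at time of initial follow up to screen for possible urinary tract infection". Four symptom questions follow, on pain, frequency, lower abdominal pressure, and colour or smell; the first is "Have you had any pain with urination". The consequence of a positive screen is "If screen positive, will order urinalysis and urine culture".

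The only record abstraction described is before surgery: "Existing pre-operative laboratory testing will be abstracted from the subjects' medical record". The list under Demographics, Patient Specifics includes preoperative UTI and discharge destination (home or rehabilitation facility). It has no field for postoperative antibiotics, outside urine results or care received after discharge.

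The protocol does not say what makes a case (symptoms, urinalysis, culture or treatment), gives no positivity threshold, and does not date the initial follow-up visit.

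**The concern.** A patient may go home or to a rehabilitation facility, develop symptoms, be diagnosed by another clinician and finish treatment before the study visit. The symptom questions may pick this patient up, but the only step that follows is a urine test at that visit, and a treated infection may no longer show. Nothing else in the plan is set up to record it.

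UTI matters to the interpretation of this trial. The Background and Introduction lists it among the adverse events associated with retention. It also says of the intermittent and indwelling catheters used to treat retention, "both of which are associated with an increased prevalence of postoperative urinary tract infection". A UTI can therefore plausibly arise in either arm, and readers will want a reliable count in both. Information that the questionnaire never asks for cannot be recovered at analysis.

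**Working it through.** **1. Plan's own figure (context only).** The plan gives 194 per group, 388 in all and 432 after 10% drop-out. Inputs are the cited hip arthroplasty trial's retention rates ("They found a 2.8% rate of urinary retention in patients who received a urinary catheter and a 9.7% rate in patients who did not"). Two-sided alpha of 0.05 and 80% power are assumed, since the plan states neither.

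n = [1.96·√(2·p̄(1−p̄)) + 0.842·√(p1(1−p1) + p2(1−p2))]² / (p1−p2)²

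This gives 193 per group for 2.8% v 9.7%, and 194 for 3% v 10%. Then 388 / 0.90 = 431.1, rounded up to 432. The stated size reproduces. It rests on retention, not UTI.

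**2. What each route can reach.**

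| Situation | Item 4a | Item 4b |
|---|---|---|
| Infection present at the second straight catheterization or catheter placement | Urinalysis sent | Not needed |
| Infection still active at the follow-up visit | Not reached | Reached if symptoms are reported |
| Infection arising later than any 4a test, diagnosed and treated before the visit | Not reached | Symptoms may be reported; the urine test may be negative; no question on diagnosis or antibiotics |

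The third row is the gap.

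**3. How many patients depend on item 4b.** Assume that item 4a refers to postoperative placement. Its triggers are then those that define retention in item 1. Assume also that the planning rates apply to that definition.

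- Group 1: 194 × 0.028 = 5.4 patients tested in hospital, so 97.2% depend on the visit.
- Group 2: 194 × 0.097 = 18.8 patients tested in hospital, so 90.3% depend on the visit.

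**4. What under-capture could do (illustration only).** The UTI rates and the shares missed are assumptions. Let a share s be missed equally in both arms. Each rate becomes p(1−s), the difference becomes (pA−pB)(1−s), and the ratio pA/pB is unchanged. With 194 per arm and 5% v 2%:

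| s | Expected cases | Difference (points) | Risk ratio | Power |
|---|---|---|---|---|
| 0 | 9.7 v 3.9 | 3.0 | 2.5 | 36% |
| 25% | 7.3 v 2.9 | 2.25 | 2.5 | 28% |
| 50% | 4.9 v 1.9 | 1.5 | 2.5 | 20% |
| 75% | 2.4 v 1.0 | 0.75 | 2.5 | 12% |

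Power = Φ{[d − 1.96·√(2p̄(1−p̄)/n)] / √[(pA(1−pA) + pB(1−pB))/n]}, where d is the difference and n = 194. Over the same values of s, power falls from 29% to 23%, 17% and 10% for 3% v 1%, and from 30% to 23%, 17% and 10% for 6% v 3%. With counts this small the normal approximation is rough; only the direction should be relied on.

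**The case against.** **No exclusion rule is written.** A reader might infer that a UTI counts only if the follow-up urine test is positive, and that a treated case is entered as no UTI. The text does not say so. Item 4b describes a screen and a test order, and the protocol is silent on classification. This objection stands: the defect is an unstated definition and a missing data source, not a rule that discards treated cases.

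**The questions look back.** They have no stated window, so a patient with an earlier infection may screen positive and mention the treatment. That is possible, but no field receives the answer and no rule says that it counts.

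**UTI is not presented as the main harm of the routine catheter.** A reader might take it that way. The Background ties UTI to retention and to the catheters used to treat it, and both can occur in either arm. Purpose, hypothesis and sample size all concern retention. This also stands.

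**The gap need not explain a null UTI result.** In the illustration power is only about 36% with complete capture, and equal loss leaves the risk ratio alone. A claim that the trial would report no UTI difference because treated cases were missed goes beyond the documents. So does a claim that the more severe infections are the ones lost.

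**The remedy carries some risk.** No blinding is described, so self-report and outside diagnosis could differ by arm. This stands and shapes the fix.

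**Conclusion.** The point holds as an ascertainment gap. The protocol has no UTI case definition and no stated means of capturing an infection diagnosed and treated between surgery and the initial follow-up visit, so some UTIs in either arm may be missed. The effect would be fewer events and a smaller absolute difference, with the risk ratio unchanged if the loss is equal between arms. Equal loss is itself an assumption.

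The size cannot be estimated from the documents: they give no UTI rate, no share treated early and no visit date. The figures above show direction only. UTI is in effect a secondary outcome, and no stated figure changes. The gap still deserves correction, because it is cheap to close during data collection and cannot be reliably repaired at analysis.

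**What to change.** 1. Add one item to the 4b questionnaire, asked identically in both arms: whether, since surgery, the patient has been diagnosed with a urinary infection or given antibiotics for one. If yes, obtain the test result or prescription.
2. Define the UTI outcome as a documented UTI from surgery to the initial follow-up visit, or a positive culture at that visit. State the positivity threshold and what counts as documentation.
3. Record the date and source of each case (in hospital, outside clinician, follow-up visit).
4. Report culture-confirmed cases separately from diagnoses based on treatment alone, by arm, so that any difference in reporting or outside diagnosis in an apparently unblinded trial can be seen.

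The cost is one questionnaire line, a few data fields (case, date, source) and a record request for each patient who answers yes. The downside is that some outside diagnoses will lack a culture; step 4 keeps these visible. The sample size is unaffected.
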